**Document History:**

Version No.	Date	Chapter / Attachment	Reason for Review / Modification
0.1	29.06.2022	n.a.	n.a.
0.2	06.07.2022	All chapters	Comments project team
0.3	07.07.2022	All chapters	Comments project team
0.4	20.09.2022	All chapters	Comments project team
0.5	28.09.2022	All chapters	Review cycle in the project team
1.0	30.09.2022		Final

**Abbreviations**

Abbreviation	Definition
ANCOVA	Analysis of Covariance
Brief IPQ	Brief Illness Perception Questionnaire
CI	Confidence interval
CSSRI	Client Sociodemographic and Service Receipt Inventory
EFS	Evaluated for Safety Set
FAS	Full Analysis Set
GAD-7	Generalized Anxiety Disorder Scale (7 items)
IEC	Independent Ethics Committee
ITT	Intention-To-Treat principle
IRB	Institutional Review Board
LOCF	Last Observation Carried Forward
NMAR	Not Missing At Random
PD	Protocol Deviation
PHQ-9	Patient Health Questionnaire (Depression severity, 9 items)
PP	Per Protocol
SAP	Statistical Analysis Plan
SCID-5-CV	Structured Clinical Interview for DSM-5 Disorders
SSS-8	Somatic Symptom Scale (8 items)
USE	Usefulness Scale
VAS	Visual Analogue Scale

## 1 Introduction

This Statistical Analysis Plan (SAP) is based on the published study protocol (Sikorski et al., 2021) and follows the guideline for statistical analysis plans (Gamble et al., 2017)

Some aspects of the statistical methods and the study design are already described in the study protocol. This SAP aims to further specify the procedures and statistical methods applied during the analysis of the study data.

The description of the health economic evaluation is not subject of this SAP.

### 1.1 Background and Rationale

Depression is one of the most disabling disorders worldwide, yet it often remains undetected. One promising approach to address both early detection and disease burden is depression screening followed by direct feedback to participants. Evidence suggests that individuals often seek information regarding mental health on the internet. Thus, internet-based screening with automated feedback has great potential to address individuals with undetected depression.

### 1.2 Study Objective

The study objective is to determine whether automated feedback after internet-based depression screening reduces depression severity as compared to no feedback.

**Primary Hypothesis:** The depression severity 6 months after screening is lower in at least one of the two feedback study arms (STANDARD FEEDBACK and/or TAILORED FEEDBACK) as compared to the NO FEEDBACK study arm.

**Secondary Hypothesis:** The depression severity 6 months after screening is lower in the TAILORED FEEDBACK arm as compared to the STANDARD FEEDBACK arm.

### 1.3 Study Endpoint(s)

#### 1.3.1 Primary Endpoint

The primary endpoint of the study is the change in self-reported depression severity total score from baseline to six months after randomization, measured via the Patient Health Questionnaire-9 (PHQ-9; Kroenke et al., 2001; Löwe et al., 2004). The PHQ-9 consists of 9 items and is scored on a 4-point Likert scale (0–3), resulting in a total score ranging from 0 to 27 (0 = best, 27 = worst).

#### 1.3.2 Secondary endpoints

- PHQ-9 total score change from baseline to one month after randomization.
- Depression diagnosis by a health care professional, resulting in a binary variable (yes / no), measured by self-report 6 months after randomization.
- Guideline-based depression care, using a self-developed questionnaire (psychotherapy and/or medication), based on the German National Clinical Practice Guideline for Unipolar Depression (DGPPN et al., 2015), resulting in a binary variable (yes / no), measured 6 months after randomization.

- Depression-related health behaviour, using a self-developed questionnaire (information-seeking, seeking social support, self-management, seeking formal help), resulting in a binary variable (yes / no), 6 months after randomization.
- Health-related quality of life will be assessed using the EuroQol-5D (EQ-5D-5L, Ludwig et al., 2018) six months after randomization, change from baseline. The EuroQol-5D index-value is generated using 5 dimensions: mobility, self-care, activity, pain and anxiety (each on a 5-point scale: 1 = best, 5 = worst). In addition, a visual analogue scale (VAS) is assessed.
- Anxiety severity measured via the 7-item Generalized Anxiety Disorder total score change (GAD-7, Spitzer et al., 2006, German version: Löwe et al., 2008) six months after randomization, change from baseline.
- Somatic symptom severity measured via the 8-item Somatic Symptom Scale total score (SSS-8, Gierk et al., 2014) six months after randomization, change from baseline.

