## 2.6 Timing of Outcome Assessments

**Table 1. Measures and assessment time points for endpoints**

Measures	T0	T1	T2	T3
Primary outcome				
Depression severity, PHQ-9	x		x	x a
Secondary outcomes / other outcomes				
Depression diagnosis by a health care professional				x
Guideline-based depression care (psychotherapy and/or medication)				x
Depression-related health behaviour (e.g. information-seeking)				x
Anxiety severity, GAD-7	x			x
Somatic symptom severity, SSS-8	x			x
Health-related quality of life, EQ-5D-5L	x			x
Illness beliefs, Brief IPQ	x		x	x
Intervention adherence	x			
Critical life events				x b
Depression diagnosis, SCID		x b		x b
Adverse events				x b
Characteristics				
Sociodemographic data	x			
Medical data	x			
Risk factors for depression onset	x			

*Note.* T0 = before randomisation (The randomization takes place immediately after the T0 assessments are performed); T1 = 2 days after randomisation; T2 = 1-month follow-up, T3 = 6-months follow-up; PHQ-9 = Patient Health Questionnaire-9; EQ-5D-5L = EuroQol-5D 5-L; GAD-7 = Generalized Anxiety Disorder-7; SSS-8 = Somatic Symptom Scale-8; SCID = Structured Clinical Interview for DSM-5 Disorders; Brief IPQ = Brief Illness Perception Questionnaire.

a Primary outcome; b Measures assessed via telephone interview.

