### 3.3 Analysis Populations

#### Full Analysis Set (FAS)

The primary analysis is based on the full analysis set (FAS). It is as complete as possible and as close as possible to the Intention-To-Treat (ITT) principle which includes all randomized participants, as belonging to their randomization arm, regardless of whether they received the feedback or not, or whether other protocol violations are known. For the FAS at least a valid baseline and one valid post-baseline value of the primary outcome needs to be available.

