### Secondary Outcome

The following secondary endpoints are continuous outcomes. For these, difference from baseline (T0) is calculated for 1 month (T2; PHQ-9 only) and 6 months after randomization (T3, all outcomes):

- PHQ-9 total score (9 items)
- GAD-7 total score (7 items)
- SSS-8 total score (8 items)
- EQ-5D-5L (index-value, VAS)

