## 5.2 Missing Data

The multilevel modelling approach limits the bias when handling missing data even in the case of not missing at random (NMAR).

As a sensitivity analysis missing values are imputed by different approaches for the primary analysis. In the FAS population no baseline value is missing as per definition. In case of missing follow-up values,

we conduct last observation carried forward (LOCF) and multiple imputation. In the LOCF approach, missing values are replaced by the previous valid value. The imputation model in the multiple imputation approach includes all baseline characteristics of participants and all variables of the primary outcome analysis. From the baseline values of the secondary outcomes, we include as many variables in the imputation model as possible. For the imputation of missing follow-up values, 100 imputed data sets are generated, and the results are combined using Rubin's Rules.

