#### Analysis of Secondary Endpoints

The secondary endpoint analyses are performed in the respective FAS population. All secondary endpoints are compared and statistically assessed for descriptive purposes and not in a confirmatory sense. The aim of the analysis is an exploratory data analysis, not hypothesis testing or generation of evidence for the efficacy. No attempt is made to adjust for the p-values for multiple testing.

Mean, standard deviation, first and third quartile, minimum and maximum for the continuous variables and absolute and relative frequencies for the categorical and binary variables are presented both overall and separately for the randomized groups for each time point. Number of missing observations are presented for the randomized groups separately for each time point. All summary tables are structured with a column for each group (tailored feedback, standard feedback, no feedback) and a total column.

Multilevel linear models with differences from baseline as outcome, incorporating the participants as a random term, are applied to the repeated measures in the same participant, including the factor group, time point, and the baseline value as a covariate. The interaction between time and the group is determined. If it is not significant, it is eliminated from the model. Adjusted means with 95% confidence intervals (CI) and p-values are reported.

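### Six of the seven secondary endpoints have T3 as their only follow-up value, so the missing-data assurance in SAP 5.2 does not apply to them and the T2 PHQ-9 of FAS members lost by T3 goes unused

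*SAP*

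**What the plan says.** **Timing.** SAP 1.3.2 lists seven secondary endpoints. One is at one month: "PHQ-9 total score change from baseline to one month after randomization". The other six are at six months. They include "Anxiety severity measured via the 7-item Generalized Anxiety Disorder total score change" and, for professional diagnosis, a binary answer "measured by self-report 6 months after randomization". Section 5.1 sets the change scores of the continuous secondary endpoints at "1 month (T2; PHQ-9 only) and 6 months after randomization (T3, all outcomes"). Table 1 agrees, with "T2 = 1-month follow-up, T3 = 6-months follow-up".

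**Population.** Section 3.3: "For the FAS at least a valid baseline and one valid post-baseline value of the primary outcome needs to be available". Section 5.3: "The secondary endpoint analyses are performed in the respective FAS population".

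**Model.** Section 5.3 (secondary endpoints) uses a linear multilevel model of the change from baseline, with group, time point, baseline value and a random participant term. It reports adjusted means, 95% intervals and p-values. For binary variables it gives frequencies and names no inferential model.

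**Missing data.** Section 5.2 opens by claiming that the multilevel approach keeps missing-data bias in check, even when values are not missing at random. It continues: "As a sensitivity analysis missing values are imputed by different approaches for the primary analysis". The methods are LOCF and multiple imputation with 100 data sets. No imputation is planned for the secondary endpoints.

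**The concern.** A multilevel model helps with missing data when a participant who lacks one follow-up value has another that informs it. The primary endpoint has this, because PHQ-9 is taken at T2 and T3. The six endpoints above do not. The general statement in 5.2 therefore offers an assurance that the planned analysis cannot give for most of the secondary endpoints.

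Useful information does exist. A FAS member without a T3 PHQ-9 must have a T2 PHQ-9, a recent measure of symptoms in the very people who drop out of the T3 analyses. Participants know their allocation (SAP 2.2), so it is plausible that the reasons for leaving after one month differ by arm. If they do, the arm comparisons at T3 are selected on one-month symptoms, and adjusting for the outcome's own baseline does not remove that.

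**Working it through.** **1. Follow-up values per endpoint (SAP 1.3.2, 5.1, Table 1)**

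| Secondary endpoint | T0 | T2 | T3 |
|---|---|---|---|
| PHQ-9 change to one month | x | x | (primary) |
| GAD-7 | x | – | x |
| SSS-8 | x | – | x |
| EQ-5D-5L (index, VAS) | x | – | x |
| Professional diagnosis | – | – | x |
| Guideline-based care | – | – | x |
| Health behaviour | – | – | x |

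Six of seven have T3 only.

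**2. What the 5.3 model becomes.** The outcome is the change score and baseline is a covariate, so T0 is not a repeated outcome. Each participant gives at most one row for GAD-7, SSS-8 or EQ-5D-5L. The participant term, the time factor and the time-by-group interaction then have nothing to estimate. What remains is an ANCOVA on those observed at T3.

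**3. Who is left out.** The plan's own numbers first: 233/(1 − 0.35) = 358.5 (SAP 2.3 states 358), and 3 × 358 = 1074. At 35% drop-out, 0.65 × 1074 = 698 have T3 and 376 do not. Let q be the share of those 376 with a T2 PHQ-9. The SAP does not give q, so it is an assumption.

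| q | In FAS without T3 | FAS | Share |
|---|---|---|---|
| 0.1 | 38 | 736 | 5% |
| 0.3 | 113 | 811 | 14% |
| 0.5 | 188 | 886 | 21% |
| 0.7 | 263 | 961 | 27% |
| 1 (upper limit) | 376 | 1074 | 35% |

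**4. Size of the bias for a continuous scale (all inputs assumed).** Let ρ be the correlation of T2 PHQ-9 with the T3 outcome given baseline, p the share missing at T3, and b₁ and b₀ the log odds of missing T3 per SD of T2 PHQ-9 in a feedback arm and in the control arm. To first order, the mean T2 residual among those observed shifts by −b·p, so

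bias ≈ −ρ × p × (b₁ − b₀).

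With ρ = 0.5, p = 0.15, b₁ = 0.5 and b₀ = 0, this is −0.5 × 0.15 × 0.5 = −0.0375. If the true effect is −0.20 SD, the estimate is about −0.238. When the slope and the missing share are the same in both arms, the bias is about zero.

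A large simulation with true effect −0.20 SD gives these observed-case estimates:

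| ρ | Nominal p | Same in both arms (b = 0.4) | One arm only (b₁ = 0.5) | Opposite (b₀ = 0.5, b₁ = −0.5) |
|---|---|---|---|---|
| 0.3 | 15% | −0.203 | −0.221 | −0.158 |
| 0.5 | 15% | −0.193 | −0.238 | −0.117 |
| 0.7 | 15% | −0.195 | −0.253 | −0.090 |
| 0.3 | 35% | −0.195 | −0.250 | −0.100 |
| 0.5 | 35% | −0.193 | −0.283 | −0.025 |
| 0.7 | 35% | −0.198 | −0.304 | +0.045 |

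Estimates that use T2 PHQ-9 lie between −0.207 and −0.195 in all these cells. The 15% rows are close to q = 0.3. The 35% rows need nearly every drop-out to have T2, so they are an upper limit. The bias can inflate or shrink the effect.

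**The case against.** The strongest reply is that the SAP calls these analyses exploratory and descriptive (3.1, 5.3), and that keeping imputation for the confirmatory endpoint is a common choice. This stands as a reason for modest weight. It does not remove the point, because exploratory status deals with multiplicity and not with selection, and 5.3 still reports adjusted means, intervals and p-values.

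Five further limits stand:

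- The bias needs arm-dependent loss, on which the SAP has no data. With 233 observed per arm, the standard error of an arm difference is about √(2/233) = 0.09 residual SD, so the lower part of the range is within one standard error.
- A reader might infer that all 35% of drop-outs are affected. Drop-outs without T2 are outside the FAS, and this repair does nothing for them.
- A reader might infer that every FAS member lacking a T3 scale has T2 data. The FAS rule guarantees this only when the T3 PHQ-9 itself is missing. Someone who answers the T3 PHQ-9 but not the GAD-7 need not have T2, and nothing guarantees a T2 Brief IPQ.
- A reader might infer that the primary endpoint is fully protected and the others not at all. Imputation of the primary endpoint is only a sensitivity analysis, and its model as described in 5.2 does not name T2 PHQ-9.
- It would be too strong to say that no planned analysis could give a signal. Missing counts by group and the PHQ-9 imputation analyses might. The drop-out regression in 5.5 lists baseline variables only.

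**Conclusion.** The point holds as a gap in 5.2 of moderate weight. Section 5.2 gives a general assurance that cannot apply to six of the seven secondary endpoints, and the plan leaves unused the one-month PHQ-9 of FAS members who lack a T3 PHQ-9. That the analysis is observed-case follows from 5.1, 5.2 and 5.3 together; the SAP does not use the term.

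The documents do not support saying that these estimates are biased, only that they would be if loss at T3 depended on one-month symptoms differently by arm. Under the assumptions shown, with about 15% of the FAS lost after T2, the bias on a scale is 0.02 to 0.05 SD for dependence in one arm and 0.04 to 0.11 SD for opposite dependence. With the same dependence in every arm it is about zero. These sizes cover the continuous scales only. They say nothing direct about the three binary endpoints, for which 5.3 names no inferential model. Nor should they be read as a share of the planned effect, because f = 0.118 in 2.3 belongs to the primary outcome and the SAP sets no target effect for the other scales.

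**What to change.** In 5.2, limit the multilevel missing-data statement to endpoints with more than one follow-up value, and say that the T3-only endpoints are analysed on observed T3 values.

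In 5.2 and 5.3, add a sensitivity analysis for FAS members: multiple imputation (100 data sets, Rubin's Rules) of GAD-7, SSS-8, EQ-5D-5L index, EQ-5D VAS and the three binary endpoints at T3. The imputation model should include arm, the outcome's own baseline where measured, baseline PHQ-9 and, named explicitly, T2 PHQ-9. T2 Brief IPQ items are optional. Report the imputed result beside the observed-case result.

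The cost is some SAP wording, programming and output; no new data are needed. The imputed result still assumes that T3 values are missing at random given T2, and this should be stated with it.

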### 1.3.3 Other endpoints

- Illness beliefs regarding depressive symptoms will be measured with a modified version of the well validated Brief Illness Perception questionnaire (Brief IPQ, Broadbent et al., 2006) and analysed per domain / item.
- Major depression diagnosis evaluated with the Depression related modules of the Structured Clinical Interview for DSM-5 Disorders (SCID-5-CV, Beesdo- Baum et al., 2019). Interviews will be conducted via telephone by a trained assessor. Sum score of number of critical life events: Two open questions assessing relevant positive and negative critical life events will be asked by phone 6 months after randomization and summed up.

### 1.3.4 Safety endpoints

To estimate possible unintended adverse events of the feedback intervention, participants are asked about the occurrence of any negative event that is attributed to the trial with an open question six months after randomization. Adverse events will be categorized by the investigator.

### 1.3.5 Participants characteristics

Participant characteristics recorded before randomization include

- sociodemographic data (e.g. age, gender, education, family status, rural/urban area living, local residency),
- medical data (diagnosis of and treatments for depression) and
- risk factors for depression onset (e.g. chronic somatic comorbidities, pregnancy, alcohol and nicotine consumption).

Domain	German question	Notes
Rural/urban area living	Wie groß ist die Stadt, in der Sie leben? In welchem Bundesland leben Sie?	
Demographic data	Wie sind Sie krankenversichert? Wie groß sind Sie (ggf. schätzen)? Wie schwer sind Sie (ggf. schätzen)?	
Local residency	Was ist Ihre Muttersprache? Was ist Ihre Staatsangehörigkeit?	
	Würden Sie sich selbst als Migrant/in bzw. Person mit Migrationshintergrund bezeichnen?	
Gender	Was ist Ihr Geschlecht?	
Age	Wie alt sind Sie?	

Family status	Was ist Ihr Familienstand? Wie ist Ihre Wohn- / Lebenssituation?	
Education	Was ist Ihr höchster Schulabschluss?	Summarized into 3 categories
	Was ist Ihr beruflicher Status? Besteht im Moment oder bestand in den letzten sechs Monaten ein reguläres Arbeitsverhältnis (außer Minijob)?	
Nicotin consumption	Rauchen Sie (Zigaretten, E-Zigaretten, Zigarillos, Pfeife)? Wie viele Zigaretten (bzw. E-Zigaretten, Zigarillos, Pfeifenköpfe, etc.) rauchen Sie am Tag? Seit wie vielen Jahren rauchen Sie (wenn Sie weniger als 1 Jahr rauchen, geben Sie bitte 0 ein)?	
Alcohol consumption, AUDIT-C	Wie oft trinken Sie Alkohol? Wenn Sie an einem Tag Alkohol trinken, wie viele alkoholhaltige Getränke trinken Sie dann typischerweise? Wie oft haben Sie im letzten Jahr an einem Tag 6 oder mehr alkoholische Getränke getrunken?	sum score
Risk factor score	Leiden Sie unter Ängsten? Leiden Sie unter einer Sucht (Drogen, Computerspielsucht, Spielsucht, etc.)? Hatten Sie in der Vergangenheit ein Lebensereignis, das Sie bis heute belastet? Leiden Sie seit mindestens sechs Monaten unter anhaltenden körperlichen Beschwerden (z.B. Rückenschmerzen, Kopfschmerzen, Übelkeit)? Litten Sie im letzten Monat unter Stimmungsschwankungen oder gedrückter Stimmung? Haben Sie (eine) chronische körperliche Erkrankung(en) (z.B. Herzerkrankung, Diabetes, Asthma, etc.)? Fühlen Sie sich von Ihrem sozialen Umfeld unterstützt? (invert) Wurde bei Ihnen die Diagnose einer anderen psychischen/seelischen Erkrankung gestellt? Haben Sie Familienmitglieder, die unter psychischen Beschwerden leiden (z.B. Depressionen, Ängste, Essstörungen, Suchterkrankungen)? Gibt es in Ihrer Familiengeschichte bekannte Fälle von Suiziden oder Suizidversuchen? Versuchen Sie im Moment schwanger zu werden? Sind Sie momentan schwanger? Haben Sie in den letzten 6 Monaten entbunden? Stillen Sie momentan? Leiden Sie unter prämenstruellen Störungen (PMS)? Befinden Sie sich in Ihrer Menopause?	sum score
Somatic morbidity score	Um welche chronische(n) Erkrankung(en) handelt es sich? Herzerkrankung Diabetes Atemwegserkrankungen (z.B. Asthma, COPD, etc.) Darmerkrankungen Neurologische oder Nervenerkrankungen (z.B. Multiple Sklerose, Schlaganfall, etc.) Schmerzerkrankungen Krebs	sum score

	Rheumatologische Erkrankungen und/oder Gelenkerkrankungen sonstige Erkrankung(en)	
Depression history	Wurde bei Ihnen jemals die Diagnose Depression oder Burnout gestellt?	
	Wer hat die Diagnose erstmalig gestellt und Ihnen vermittelt?	
	Wann waren Sie das letzte Mal aufgrund von Depressionen oder Burnout in Behandlung?	
	Um welche Art der Behandlung handelt(e) es sich?	
	Können Sie sich vorstellen, aktuell an einer Depression zu leiden?	
Comorbidities	Wurde bei Ihnen die Diagnose einer anderen psychischen/seelischen Erkrankung gestellt?	
	Haben Sie (eine) chronische körperliche Erkrankung(en) (z.B. Herzerkrankung, Diabetes, Asthma, etc.)?	
Potential treatment preference	Wenn Sie vermuten würden, an einer Depression zu leiden, welche/n Behandler/in würden Sie als erstes aufsuchen?	

## 2 Study Methods

### 2.1 Trial Design

The DISCOVER trial is designed as an internet-based, observer-blinded, stratified randomized controlled clinical trial with three parallel groups (1:1:1), which is conducted nationwide in Germany.

Study arms:

- No feedback: The participants do not get any feedback on their screening result.
- Standard feedback: Participants receive standardized feedback comprising the following four sections 1) the depression screening result, 2) a note to seek diagnostic consultation by a health professional, 3) brief general information on depression and 4) information on depression treatment.
- Tailored feedback: Participants receive standard feedback tailored to their individual symptom profile, illness perceptions and preferences. Details regarding the tailored feedback arm are described in the published study protocol.

### 2.2 Randomization and Blinding

Randomisation is based on a computer-generated randomization sequence (1:1:1 allocation ratio), which was conducted by an independent researcher of the Department of Medical Biometry and Epidemiology and is not accessible to any other study team member. The sequence consists of permuted blocks of randomly arranged sizes (6, 9 and 12) and is stratified by baseline depression severity (moderate: PHQ-9  $\geq 10$  and  $\leq 14$  points; severe: PHQ-9  $\geq 15$  points). Allocation is performed by a computerized system, ensuring allocation concealment.

Individuals who participate multiple times are automatically allocated to the same study arm as before. This process is ensured by a privacy-preserving record linkage service which identifies double entries based on personal data.

Participants know their allocation due to the nature of the intervention but are kept unaware of trial hypotheses to minimise expectancy bias. The research staff assessing outcomes in the telephone interviews are blind to the allocation at any time.

